2 STUDY OBJECTIVES (PARTS B, C, AND D)

2.1 Primary Objective

- Assessment of the safety and tolerability of PLN-74809

2.2 Secondary Objectives

- Assessment of PK of PLN-74809

2.3 Exploratory Objectives

- █ [REDACTED]
- █ [REDACTED]
- █ [REDACTED]
- █ [REDACTED]

3 INVESTIGATIONAL PLAN

3.1 Overall Study Design and Plan

This is a Phase 2a, multicenter, 4-part, randomized, double-blind, dose-ranging, placebo-controlled study to evaluate the safety, tolerability, and PK of once-daily (QD) treatment with PLN-74809 in participants with IPF. The 4 parts of the study are summarized in [Table 1](#).

Each study part consists of an up to 28-day screening period, a treatment period, and a 2-week post-treatment follow-up period; see study schematic in [Figure 1](#) (Part B), [Figure 2](#) (Part C), and [Figure 3](#) (Part D).

Table 1 Overview of Parts A, B, and C of Study PLN-74809-IPF-202

Study Part	Duration (Weeks)	PLN-74809 Formulation	Randomization (active:placebo)	Dose (mg) Regimen (QD)
A	4	██████████	1:1:1 per treatment group	20/40/0
B	12	██████████	3:1 per treatment group	40/0
Following review of clinical data from Part B				
C	12	██████████	3:3:2 per treatment group	80/160/0
Following review of clinical data from Part C				
D	At least 24	██████████	3:1 per treatment group	320/0

QD = once daily

Part A enrollment has been completed, so is not further described herein; no further participants will be enrolled or treated in this part of the study.

Part B enrollment has been completed; no further participants will be enrolled or treated in this part of the study.

Part C enrollment was initiated following Data Safety Monitoring Board (DSMB) review of the clinical data supporting the evaluation of 40 mg dosing. The DSMB recommended continuation of Study PLN-74809-IPF-202 to evaluate doses of 80 mg and 160 mg without modification.

Part D enrollment will initiate following DSMB review of the 80 mg and 160 mg clinical data from Part C. The dose level of Part D is supported by the clinical data from study ██████████ and the duration is supported by the chronic toxicology data.

Please refer to the Investigator's Brochure for additional detailed information on chronic toxicology studies.

Figure 1 Study Schematic for Part B of Study PLN-74809-IPF-202

[figure not shown]

Figure 2 Study Schematic for Part C of Study PLN-74809-IPF-202 (Parallel Dosing)

[figure not shown]
[figure not shown]

Figure 3 Study Schematic for Part D of Study PLN-74809-IPF-202

QD = once daily

* Treatment will continue for all participants in Part D until the last participant enrolled in Part D reaches Week 24. All participants will complete visits every 8 weeks after the Week 24 visit until such time as the last participant enrolled has completed the Week 24 visit. At this time, all participants will be contacted to return and complete the Final On-Treatment Visit. All participants will have a Week 26 visit, which will be considered the End of Treatment Visit for the last participant to complete the Week 24 Visit.

Potential participants who provide written informed consent will be screened for study eligibility up to 28 days before administration of the first dose of study drug.

In Parts B, C and D, eligible participants will be randomized on Day 1 (Visit 2). Randomization will be stratified by use of SoC IPF therapy with pirfenidone or nintedanib (SoC use; yes or no).

In Part B, 29 eligible participants were randomized in a 3:1 ratio (active:placebo) and treated for 12 weeks.

In Part C, approximately 56 eligible participants will be randomized in a 3:3:2 ratio (80 mg PLN-74809:160 mg PLN-74809:placebo) and treated for 12 weeks in parallel treatment groups.

In Part D, an additional PLN-74809 dose of 320 mg is planned for evaluation based on the following criteria:

- Part C has been completely enrolled (ie, 56 participants have been randomized)
- Pending favorable review by the DSMB of:
 - All available safety and PK data from this study (Part C)
 - Safety and PK data from study [REDACTED], as described in the Investigator’s Brochure

In Part D, approximately 28 eligible participants will be randomized in a 3:1 ratio (320 mg PLN-74809:placebo) on Day 1 (Visit 2). Randomization will be stratified by use of SoC IPF therapy (pirfenidone or nintedanib) (SoC use; yes or no). Study treatment will be administered for at least 24 weeks. Treatment will continue for all participants in Part D until the last participant enrolled in Part D reaches Week 24.

In Parts B and C, study drug will be administered at the investigational site on Day 1 and at Weeks 4 and 12. In Part D, study drug will be administered at the investigational site on Day 1 and at Weeks 4, 12, and 24. Participants will self-administer the study drug on an outpatient basis on all other days. In Parts B and C, participants will return to the study site for on-treatment evaluations on Day 1 and at Weeks 2, 4, 8, and 12 (see Schedule of Events in [Appendix 1](#)).

In Part D, participants will return to the study site for on-treatment evaluations on Day 1 and at Weeks 2, 4, 8, 12, 14, 20, 24, 26, and every 8 weeks after Week 24 until the last participant enrolled in Part D has completed this Week 24 visit. At this time, all participants will be contacted to return and complete the Final On-Treatment Visit (see Schedule of Events in [Appendix 2](#)). Blood and urine specimens for safety laboratory assessments will be collected after at least an 8-hour fast. A final study visit will be conducted 2 weeks \pm 3 days after the last dose of study drug (Week 14 \pm 3 days for Parts B and C; 2 weeks after the final On-Treatment Visit [\pm 3 days] for Part D), when participants will undergo a final [REDACTED] measurement, as well as follow-up end of study (EoS) evaluations.

Participants who discontinue study drug for safety reasons prior to completion of 12 weeks (Parts B and C) or at least 24 weeks (Part D) of treatment will be asked to remain in the study to complete all remaining assessments; if this is not feasible, they will be asked to return to the clinic for an Early Termination (ET) visit for follow-up evaluations.

[REDACTED] measurements will be obtained via spirometry and will be performed using study-standardized equipment and according to international guidelines (American Thoracic Society [ATS]/ European Respiratory Society [ERS]/ Japanese Respiratory Society [JRS]/ Latin American Respiratory Society [ALAT]). Spirometry reading will be centralized.

[REDACTED]
[REDACTED]
The DSMB will assess participant safety at predetermined intervals during the study, including prior to initiating Part D and following the enrollment of the last participant in Part D. [REDACTED]
[REDACTED]

The total number of participants enrolled in Parts B, C, and D of the study will be approximately 112, with approximately 84 receiving PLN-74809 and 28 receiving placebo.

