6.2 Dose Modifications and Interruptions

There will be no dose modifications of the study drug. If the study drug needs to be interrupted for safety or tolerability issues, this should happen, as feasible, in consultation with the Medical Monitor and Study Director, who together with the Investigator will assess and decide whether the study drug interruption should be temporary or permanent on a case-by-case basis. Participants who discontinue study drug for safety reasons prior to completion of 12 weeks of treatment will be asked to remain in the study to complete all remaining assessments; if this is not feasible, then they will be asked to return to the clinic for an early termination visit.

Dose modifications or interruptions of pirfenidone or nintedanib treatment may be implemented only for safety and tolerability reasons [REDACTED], in accordance with their corresponding prescribing information and in consultation with the Medical Monitor and Study Director. This should not affect the administration of the study drug or the continuation of participants in the study.

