11 EARLY DISCONTINUATION OF STUDY OR INDIVIDUAL PARTICIPANTS

In accordance with the Declaration of Helsinki, participants have the right to withdraw from the study at any time for any reason. The Investigator or Sponsor may withdraw a participant from the study or discontinue study drug for any of the following reasons:

- Noncompliance with protocol procedures including those relating to administration of study drug
- A serious or intolerable AE occurs
- Infection with COVID-19 that precludes safe participation in the study
- A clinically significant change in a laboratory parameter occurs
- [REDACTED]
- [REDACTED]
- The Sponsor or Investigator terminates the study
- The participant requests to be discontinued from the study

If a participant is withdrawn from the study or discontinues study drug, they will undergo early termination assessments; refer to the Schedule of Events for Parts B and C ([Appendix 1](#)) and Part D ([Appendix 2](#)).

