6.1.6 Efficacy Intent-to-Treat Population

The Efficacy Intent-to-Treat (ITT) Population includes all randomized participants.

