6.2.4 Early Termination Assessments

Early termination assessments will not be summarized. Early termination assessments will appear in the listings as recorded.

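### Follow-up after stopping study drug depends on the reason for stopping, and Protocol Sections 3.1, 6.2 and 11 do not give one consistent rule

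*Protocol*

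**What the plan says.** Three protocol sections deal with what happens after a participant stops study drug.

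- **Section 3.1** (and the synopsis) addresses "Participants who discontinue study drug for safety reasons prior to completion of 12 weeks (Parts B and C) or at least 24 weeks" in Part D. These participants "will be asked to remain in the study to complete all remaining assessments", with an ET visit only where that is not feasible.
- **Section 6.2** restates the request for those who stop for safety reasons "prior to completion of 12 weeks of treatment will be asked to remain in the study". It does not carry the 24-week limit for Part D.
- **Section 11** says: "If a participant is withdrawn from the study or discontinues study drug, they will undergo early termination assessments". It makes no exception for the people Section 3.1 asks to stay. Its readable reasons for discontinuation include at least one that is not a safety reason: "Noncompliance with protocol procedures including those relating to administration of study drug".

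On analysis, SAP 6.2.4 states: "Early termination assessments will not be summarized"; they appear in listings only. SAP 6.2.8 tabulates scheduled post-baseline values only, and Protocol 7.14 rules out imputing missed assessments. Efficacy is presented mainly for a population defined in SAP 6.1.6: "The Efficacy Intent-to-Treat (ITT) Population includes all randomized participants". SAP 6.11.1 adds a mixed model for repeated measures (MMRM) on FVC change, with a difference from placebo and a p-value for each dose at each visit.

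**The concern.** Stopping drug happens after randomization and may be related to outcome. If the reason for stopping decides whether a participant is followed, then the participants with later data are a selected subset, although the population is named as everyone randomized. The arms are small, so a few such participants can matter.

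Sites also face two instructions for the same person. Someone who stops for a safety reason is kept on the schedule by Section 3.1 and given ET assessments by Section 11. In Part D, someone who stops for safety between Weeks 12 and 24 is covered by Section 3.1 but not by Section 6.2.

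The stakes are limited but real. FVC is exploratory and Protocol 12.1 tests no hypothesis, yet Section 3.2 says that the findings will inform dose selection for later IPF studies. The primary safety endpoint is touched as well, because adverse events are collected only to the participant's last study visit (Protocol 8.1, SAP 6.15.1).

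**Working it through.** **1. The instructions side by side**

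| Participant | Sections 3.1 and 6.2 | Section 11 | What reaches the by-visit tables |
|---|---|---|---|
| Stops drug for safety, able to stay | Keep the schedule | ET assessments | Scheduled visits before and after stopping, if 3.1 governs |
| Stops drug for safety, unable to stay | ET visit | ET assessments | Visits before stopping |
| Stops drug for another reason | Silent | ET assessments | Visits before stopping; later ones only if the schedule happens to continue |
| Withdraws from the study | Not addressed | ET assessments | Visits before withdrawal |

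The third row is the gap. The first row is the conflict.

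**2. Planned numbers (Protocol 3.1, 6.4, 12.2)**

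- Active: 28 × 3/4 = 21 (B); 56 × 3/8 = 21 for each dose (C); 28 × 3/4 = 21 (D). Sum 84.
- Placebo: 28 × 1/4 = 7 (B); 56 × 2/8 = 14 (C); 28 × 1/4 = 7 (D). Sum 28.
- Total 84 + 28 = 112. This reproduces the plan's figures.

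**3. Weight of one participant**

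- Dose arm: 1/21 = 4.8%.
- Pooled placebo: 1/28 = 3.6%.
- Part D placebo alone: 1/7 = 14.3%. This applies only to analyses of Part D by itself.

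**4. Total drug discontinuation (assumed rate)**

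The documents give no rate. Assume a constant 0.5% to 1% per week, so the proportion stopped by week t is 1 − exp(−rt).

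- Week 12: 1 − exp(−0.06) = 5.8%; 1 − exp(−0.12) = 11.3%.
- Week 24: 1 − exp(−0.12) = 11.3%; 1 − exp(−0.24) = 21.3%.

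**5. Share affected if Section 3.1 governs**

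Safety stoppers are asked to stay, so only non-safety stops count. Assume these are 25% to 75% of stops.

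- Week 12: 0.25 × 5.8% = 1.5% to 0.75 × 11.3% = 8.5%, or 0.3 to 1.8 of 21.
- Week 24: 0.25 × 11.3% = 2.8% to 0.75 × 21.3% = 16.0%, or 0.6 to 3.4 of 21.

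**6. What a loss would do (illustration)**

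- Precision: if a fraction d is lost in both arms, the standard error at a visit is multiplied by 1/√(1 − d). That is 1.05 at 10% and 1.12 at 20%.
- Bias: a simple observed-case difference shifts by (loss in active − loss in placebo) × (gap in mean change between lost and observed participants). With an assumed gap of 100 mL and losses of 20% and 10%, the shift is 0.10 × 100 = 10 mL. An MMRM removes this only if the data are missing at random given earlier visits.

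**The case against.** Several stronger readings are tempting, and the documents do not support them.

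- **That Section 11 takes every drug stopper out of the study.** It prescribes ET assessments; it does not say that the participant leaves or that scheduled visits end. Appendix 1 puts ET in the same column as End of Study, and Protocol 7.10 links the ET visit to leaving the study early, so a site could read it that way. That makes it an ambiguity to settle, not a stated rule.
- **That the ITT analysis, including the MMRM, certainly loses these outcomes.** SAP 6.2.4 speaks of summaries and does not mention the model. SAP 6.2.5, 6.11 and 6.11.1 are partly blacked out, so a rule bringing ET spirometry into the MMRM cannot be excluded. Visits before stopping are kept in any case.
- **That 6 to 21% of participants are affected.** That range is all drug discontinuation under the assumed rate. It includes the safety stoppers whom Section 3.1 keeps.
- **That people stopping for lack of benefit or progression are the ones lost.** Neither reason is in the readable list in Section 11, where two entries are blacked out. The visible group that a wider request would newly reach is mainly noncompliance. A participant who asks to leave the study cannot be kept by such a request.
- **That the primary safety endpoint is badly damaged.** Adverse events reported at an ET visit still count as treatment-emergent, and planned follow-up after the last dose is only two weeks for completers. Nothing shows a shorter window for non-safety stoppers, although the timing of ET is not stated.

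What stands is that the relevant sentences of Sections 3.1, 6.2 and 11 are fully readable and do not agree, and that no readable text asks non-safety stoppers to stay.

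**Conclusion.** The point holds as an inconsistency in follow-up rules with a conditional effect on the analysis. Followed as written, retention after stopping drug depends on the reason, Section 6.2 lacks the Part D limit, and Section 11 overlaps with the other two without an exception. Unless a redacted rule provides otherwise, the exploratory by-visit efficacy summaries lack values after stopping for the non-safety group, and the FVC model may lack them too. For anyone who leaves, adverse event collection stops at the exit visit.

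The size is unknown. The 1.5 to 8.5% (Week 12) and 3 to 16% (Week 24) ranges rest on an assumed weekly rate and an assumed non-safety share, and on every safety stopper agreeing to stay. No stated sample size or power claim is wrong, because none depends on this. It is a modest point that is cheap to correct.

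**What to change.** Reconcile Protocol Sections 3.1, 6.2 and 11 into one data-collection rule for the parts still running: Part D, and Part C where ongoing. Ask every participant who stops study drug, whatever the reason, to continue scheduled safety and spirometry visits through Week 12 (Part C) or Week 24 (Part D). Reserve the ET visit for withdrawal from the study. Section 6.2 should carry the same limits as Section 3.1.

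The cost is a text change in three sections and a few extra visits for those who stop drug. Part B enrollment and treatment are complete, so the change cannot help there, nor can it recover visits for any data already locked.

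Using ET values in the analysis, for instance through a visit window, is optional. It mixes off-schedule and off-drug values into visit estimates, so it is best shown as a sensitivity analysis. No change to dosing or to the criteria for stopping treatment is proposed.

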3.2 Rationale for PLN-74809 Doses and Control Group

This study will be the first to characterize the safety, tolerability and PK of PLN-74809 in participants with IPF, with or without co-administration with SoC (pirfenidone or

nintedanib). The proposed randomized, double-blind study design allows a reduction in bias in the assessment of drug safety and tolerability. Stratification for background treatment with SoC will ensure a similar proportion of participants in each treatment group. The proposed sample size and 12-week treatment duration of Parts B and C are expected to provide meaningful PK information in the IPF population, as well as allow for preliminary evaluation of dose-dependent treatment effects on [REDACTED] study endpoints, comparing PLN-74809 to placebo.

The evaluation of PLN-74809 40 mg in Part B of this study is supported by the 13-week toxicology data, safety and PK data at these doses from study [REDACTED], as well as the PD findings from study [REDACTED], where this dose led to reduction of TGF- β activation in the lungs of healthy participants following 7 days of dosing, as assessed by reduction in phosphorylated SMAD2 (pSMAD2)/SMAD2 ratio in BALF (See PLN-74809 Investigator's Brochure for more details).

The evaluation of PLN-74809 80 mg and 160 mg doses in Part C is supported by all available safety and PK data from Parts A and B, as well as safety and PK data evaluating higher doses (80 and 160 mg) from study [REDACTED].

The evaluation of PLN-74809 320 mg in Part D is supported by all available safety and PK data from Parts B and C, as well as safety and PK data evaluating the higher dose (320 mg) from study [REDACTED].

In Study [REDACTED], PLN-74809 showed a favorable safety and tolerability profile in healthy participants after single doses of up to [REDACTED] mg and after 7 days of treatment at doses of up to [REDACTED] mg (Section 1.1.2). The safety margins determined after single doses of [REDACTED] mg and multiple doses of [REDACTED] mg were calculated using the NOAEL observed in toxicology studies in [REDACTED] for both area under the plasma concentration-time curve from time zero to 24 hours (AUC_{0-24}) and C_{max} for the measured [REDACTED] of PLN-74809. At all dose levels studied, there was a [REDACTED] between the unbound AUC_{0-24} and [REDACTED] no observed adverse effect level (NOAEL). See the PLN-74809 Investigator's Brochure for more details.

Comparison of the unbound AUC_{0-24} across all doses studied in the relevant dose escalation Phase 1 studies (i.e., [REDACTED]) demonstrates that doses ranging from [REDACTED] in the SAD and [REDACTED] in the MAD remain [REDACTED] the NOAEL established in the [REDACTED] toxicology studies.

The higher dose of 320 mg to be evaluated in Part D of this study provides a reasonable escalation and separation from the 80 and 160 mg doses evaluated in Part C, allowing for appropriate dose ranging [REDACTED] (please refer to the Investigator's Brochure for further details).

Emerging data indicate that a 320 mg QD dose of PLN-74809 achieves [REDACTED] exposure, expected to provide greater levels of $\alpha_v\beta_6$ target engagement, PD response and potential clinical benefit. Interim findings from an ongoing investigation measuring uptake kinetics of the $\alpha_v\beta_6$ knottin PET radiotracer in the IPF lung indicate > 90% target saturation

at single doses of [REDACTED] mg PLN-74809 (Study PLN-74809-201). In addition, preliminary data investigating PK and PD effects in BALF from healthy participants demonstrate a dose- and concentration- dependent reduction of SMAD2 phosphorylation (a marker of reduced TGF- β signaling) when PLN-74809 was dosed at [REDACTED] mg QD for 7 days (Study [REDACTED]). These dose-dependent PD responses were associated with [REDACTED] PLN-74809 concentrations that exceeded the cell-based $\alpha_v\beta_6$ IC₅₀ (protein binding-corrected) for 6 hours (at [REDACTED] mg) or 24 hours (at [REDACTED] mg). A greater PD response is expected from a 320 mg dose, which is projected to achieve [REDACTED] concentrations that approach $\alpha_v\beta_6$ IC₈₀ at steady-state. These higher [REDACTED] exposures achieved with a 320 mg QD dose are expected to elicit increased $\alpha_v\beta_6$ target engagement and additional PD response, leading to reduced TGF- β signaling in the lung and potentially slowing the clinical progression of pulmonary fibrosis.

Part D initiation will be contingent on DSMB review of the above-mentioned data from Part C.

Findings from this study will inform dose selection for future IPF studies.

